Subjects: Subjects from the age of 16 years with documented diagnosis of asthma and/or COPD, daily treated with dry powder inhaler (DPI) or metered dose inhaler (MDI), or both, will be invited to voluntarily participate. Exclusion criteria is age <16 years, no access to use BankID or similar electronic personal identification service, not using smartphone of type Android or iPhone, plan to stop use DPI and/or MDI the following 6-12 weeks from inclusion. No able to independently handle and inhale through DPI or MDI device.

Total sample size: Eighty subjects (females and males) with daily treatment for COPD or asthma will be sufficient, based on the assumption of 25% percentage improvement in success rate of correct

inhalation technique in the interventional group compared with control group (75% versus 50%) with 80% power at 5% significance level, including dropouts at 6-12 weeks follow-up visit.

Intervention: At the baseline visit patients will be randomised to app-based intervention consisting of education and training of inhalation technique of all inhalers used on daily basis (the inhalation app-module). Stratified randomisation based on type of inhaler(s); MDI, DPI or both MDI and DPI will be applied. The intervention is the inhalation app-module, which is a medical device that is embedded the AsthmaTuner app. The AsthmaTuner app is a CE-marked cloud-based system, provided by MediTuner AB in Stockholm, Sweden. The intervention group will be instructed to use the inhalation app-module on daily basis to improve their inhalation technique.

Control group: Standard education of inhalation technique using list of standardised criteria and non-app-based education of inhaler technique.

Endpoints: Primary endpoint is the rate of subjects with successful inhalation techniques based on subjective critical endpoints (CIP Table 2) and the following objective endpoints at the 6-12 weeks follow up visit:

- DPI: PIF \geq 30 L/Min, time to PIF <0.5 seconds measured with the investigational device.
- MDI: inspiration time (> 3 seconds) and PIF less than 60 L/Min measured with the investigational device.

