Procedures: At baseline, a trained respiratory nurse will subjectively assess and train each patient's inhalation technique according to defined criteria of device handling (standard education). The AsthmaTuner app is downloaded to a smartphone or tablet computer (Ipad) that is wirelessly (Bluetooth) connected to a home spirometer. In this study the Bluetooth spirometer AsthmaTuner from MIR will be used. Education and training of inhalation technique will include measurement of inhalation flow with an adjustable resistance mounted on the spirometer, Airflow Trainer (MIR). The app gives instruction to set the resistance, so it corresponds to the selected inhaler. Questionnaires and interviews will collect information about the feasibility, safety and experienced usability of the investigational device.

Analysis: The rate of subjects with successful inhalation technique at 6–12-week visit determined by fulfilling objective and subjective critical endpoints in intention-to-treat approach. The effect of using the inhalation app-module will be analysed with logistic regression analysis across randomisation groups. The secondary analysis of feasibility and the experienced benefit of using the inhalation app-module in clinical practice and for patient's education and training of inhalation technique is estimated on a Likert scale from 1 (not at all) to 5 (strongly agree) and presented as mean and median scores.

A.2 Identification and description of the investigational device

A.2.A Description of the investigational device

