Informed consent	X	
Randomization	X	
Questionnaires of medical history and usability	X	X
Spirometry test	X	
Standard review and correction of inhalation technique	X	X
Objective assessment of inhalation technique		X
Adverse events or device deficiency		X

Randomisation

Computer-based randomisation stratified for subjects' daily inhaler use into three groups of DPI, MDI or both DPI and MDI devices of four block numbers in each stratum per investigational site.

Interview and electronic questionnaires

- A structured health questionnaire completed at the first visit will provide information regarding medical history, health care utilization and experiences of inhalation education and training, Appendix 4.

Dynamic spirometry

- The lung function test will measure forced expiratory flow in one second (FEV₁), forced vital capacity (FVC), and FEV₁/FVC according standardised procedures [31]. Applied percent of predicted reference values, adjusting for age, sex, height, weight and ethnicity, will be calculated based on continuous prediction equations of normal population [32].

Standard review of inhalation technique

- All subject's ability to handle their inhaler(s) and inhalation technique will be reviewed and corrected at baseline visit and assessed at 6–12-week follow-up visit according to endpoints in Table 2.

Investigational device - app-based intervention for education and training of inhalation technique

1. Subjects randomised to intervention will receive instructions on using the investigational device, accompanied with written information (instructions for use) from study personnel at baseline visit. The subjects are instructed to use the investigational device 3-7 times per week to achieve the maximal effect.

2. Instruction for use manual on how to use medical investigational device will be available for subjects and study personnel at investigational sites (Appendix 5). Briefly, subjects follow the following procedure:
 - a. Baseline visit: Download (Apple Store or Google Play) and login with BankID or similar to the AsthmaTuner app. Automatic Bluetooth connection will be established between the MIR AsthmaTuner and the app.
 - b. Study personnel at Karolinska institutet set up login through BankID or SITHS card to AsthmaTuner Careportal for study personnel at investigational site.
 - c. Enter patient information: Fill out patient's initial letters, study ID, height, weight and type of inhaler. Press "next" to start the test.

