The monitor and possible authorities must be given direct access to source documents (original documents, data and records). Direct access includes permission to examine, analyse, verify and reproduce any record(s) and report(s) that are important to the evaluation of the clinical study. In order to be able to do that, a written consent from each patient should be obtained. Additionally, a secrecy agreement between the monitor and the person responsible for patient records at the study site will be signed.

A.7 Statistical considerations

The analytical approach of this RCT is intention-to-treat, analyzing the effect of the investigational device across all randomized subjects with assessed inhalation technique at the 6–12-week follow-up visit. Additionally, a per-protocol analysis will be conducted on subjects who performed an inhalation test on average more than once per week during the study period, to evaluate the efficacy of education and training on inhalation technique between the intervention and control groups.

The null hypothesis of this investigation is no difference in success rate of inhalation technique between subjects assigned to intervention or control group. If the number of patients with inhalation technique deemed for correction differ significantly between intervention and control group at 5% significance level, the null hypothesis will be rejected. Based on our cross-sectional pilot study, 50% of in 40 patients with asthma demonstrated successful inhalations technique (Appendix 3), assuming +25% absolute change of correct inhalation technique in the intervention group compared with control group including 20% drop out rate, enrolment of at least 80 patients will be sufficient to reach 80% power at 5% significance level.

Primary analysis: The success rate of subjects with correct inhalation technique according to objective and subjective critical endpoints at the 6-12 weeks follow-up visit. The effect of the medical device on rate of successful inhalation technique will be determined across randomisation groups with logistic regression analysis as risk ratio (RR) with 95% confidence interval. No interim analysis will be performed.

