Secondary analyses: The analysis of feasibility and the experienced benefit of inhalation education and training support will be estimated on a Likert scale from 1 (not at all) to 5 (strongly agree), and summarized as mean and median scores. Quality content analysis will assemble collected information from questionnaire and interviews of respiratory nurses together with comments from patients. Data will be presented as categories based on oral or written quotes.

Sensitivity analysis: Analyse the rate successful inhalation technique based on objective and all subjective (not only critical) endpoints.

Descriptive statistics of the study population will be presented across the randomisation groups including information of number of randomised subjects, sex, age, asthma/COPD diagnosis, tobacco smoking status, educational level and type of inhaler(s) used for daily treatment.

The purpose of stratified block randomisation per investigational site is to adjust for imbalance in subjects' acquired knowledge of inhalation technique, common errors related to DPI and MDI devices and assessor's review of inhalation technique.

The study and the data management will be monitored by CRO, Karolinska Trial Alliance. In addition, two independent researchers ([name] and [name]) will have full access to all study information for study quality evaluation.

A.8 Data management

A CRF is used for data collection, Appendix 7. Clinical data will be entered directly into the validated electronic CRF of Research Electronic Data Capture (REDCap), stored at Karolinska Institutet, by the study personal at each site. The REDCap CRF is an online password protected database provided for the KPE Lung and Allergy department, QB:84, by Karolinska Institutet. The data entered the CRF will be validated before the clinical investigation begins.

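### The primary analysis names no term for the inhaler-type and site strata used to randomise; if those strata are prognostic, the risk-ratio interval is somewhat too wide and some power is given up

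*Protocol*

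**What the plan says.** **Allocation.** A.6.4 (Randomisation) places subjects "into three groups of DPI, MDI or both DPI and MDI devices", "of four block numbers in each stratum per investigational site". A.6.1 also describes blocks of four by inhaler type and stratified 1:1 block randomisation per site. A.1.4 lists three sites, so there are 3 x 3 = 9 cells.

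**Primary analysis.** The synopsis (A.1.5) states: "The effect of using the inhalation app-module will be analysed with logistic regression analysis across randomisation groups". A.7 says that the effect "will be determined across randomisation groups with logistic regression analysis as risk ratio (RR) with 95% confidence interval". Neither place names a stratum term, and neither rules one out.

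**Reason for stratifying.** A.7 states: "The purpose of stratified block randomisation per investigational site is to adjust for imbalance in subjects' acquired knowledge of inhalation technique". The same sentence goes on to errors specific to DPI and MDI and to the assessors' judgement of technique.

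**The concern.** Stratified blocks keep the arms alike in inhaler mix and site, so differences between strata largely drop out of the arm comparison. A model with arm alone still counts those differences as random error. Its standard error then overstates the real uncertainty: the test rejects less than 5% of the time under the null, and power is lost.

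The protocol gives grounds for expecting the strata to matter:

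- DPI and MDI have different objective success rules and different checklists (A.6.1).
- A.3 says correct technique is harder for patients who use different inhaler types, which describes the third stratum.
- Sites span primary and secondary care (A.6.1), and manual flow meters are allowed in the control arm where they are local standard care (A.6.2).
- The A.7 rationale itself treats inhaler-related errors and assessment as sources of variation worth controlling.

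At stake is a modest amount of precision in a trial that has little to spare.

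**Working it through.** **1. The plan's own figure.** Inputs from A.1.5 and A.7: 50% v 75%, 80% power, 5% level (two-sided assumed), 20% dropout, total 80.

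Per arm, n = [1.96 x sqrt(2 x 0.625 x 0.375) + 0.8416 x sqrt(0.25 + 0.1875)]^2 / 0.25^2 = (1.342 + 0.557)^2 / 0.0625, which rounds up to 58. That is 116 assessed, or 116 / 0.8 = 145 randomised. The stated 80 does not reproduce.

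With 80 x 0.8 = 64 assessed (32 per arm), power = Phi[(0.25 x sqrt(32) - 1.342) / 0.661] = Phi(0.109), about 54%. With all 80 assessed it is about 64%. This is the baseline for what follows.

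**2. Why a crude standard error is too large.** Under the null at 50%, the crude SE of the risk difference is about sqrt(0.25 x 2/32) = 0.125. A simulation with strong strata (assumed control success 66/47/15% for DPI/MDI/both, plus site differences) gave 0.1256 crude and 0.1122 with strata. The ratio is 0.1256 / 0.1122 = 1.12, so the crude SE is 12% too large. The crude critical value then acts like 1.96 x 1.12 = 2.19, an implied size of about 2.8%. The simulated size was 3.1-3.4%. With moderate strata (59/49/30%) the excess was 3%: 1.96 x 1.03 = 2.02, implied size about 4.3%, simulated 4.1%.

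**3. Stratified test against crude test.** Simulated design: 80 randomised in permuted blocks of four, 20% random loss.

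| Stratum effect (assumed) | Crude test size | Power gain, 9 cells | Power gain, inhaler type only |
|---|---|---|---|
| None | 5.2% | about -2 points | 0 |
| Moderate | 4.4% | 0 | +2 |
| Strong | 3.5% | +7 | +7 |

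**4. Regression with inhaler type and site as main effects.** Same design, 3,000 runs per row, test on the standardised risk ratio. SD is the assumed spread of each factor on the logit scale. The second column shows the control success it implies across three sites.

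| SD | Control success by site | Test size, crude / adjusted | Power, crude / adjusted | Median log-RR interval width, crude / adjusted |
|---|---|---|---|---|
| 0 | 50/50/50% | 4.0 / 5.1% | 53.1 / 55.5% | 0.81 / 0.79 |
| 0.35 | 39/50/61% | 3.6 / 5.1% | 53.7 / 58.4% | 0.81 / 0.76 |
| 0.5 | 35/50/65% | 3.3 / 4.9% | 51.3 / 58.9% | 0.81 / 0.74 |
| 0.8 | 27/50/73% | 2.5 / 5.9% | 52.0 / 64.6% | 0.81 / 0.69 |
| 1.2 | 19/50/81% | 1.7 / 6.1% | 51.3 / 74.6% | 0.80 / 0.62 |

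These gains flatter adjustment. With no stratum effect at all, power still rises by 55.5 - 53.1 = 2.4 points, only because the crude risk-ratio test sits at 4.0% and the adjusted one at 5.1%. In the last two rows the adjusted test runs at about 6%. Step 3 is therefore the more cautious guide. No row reaches 80% power.

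**5. Scale.** The claim that the interval is too wide belongs to the risk ratio, which A.7 reports. On the log-odds-ratio scale adjustment raises the standard error (0.55 to 0.62 at SD 0.5), and power rises because the estimate moves further from zero.

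**6. Sparse cells.** 64 / 9 is about 7 assessed per cell. At least one cell held a single arm in about 35% of trials in the step 3 simulation. Under other assumed mixes the share was 13% (even), 51% (50/30/20 splits on both factors) and 78% (60/25/15).

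**The case against.** The strongest reply is that the concern is read from silence. The synopsis and A.7 never say crude or unadjusted, logistic regression takes covariates, and a covariate list is commonly left to a statistical analysis plan, which is not at hand. A reader might infer that the protocol commits to an unadjusted model, and the documents do not support that. What remains is that the primary analysis is described twice by arm alone. An analysis by the randomisation groups is a specific and better method, and stating it costs nothing.

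A reader might also take the A.7 rationale to mean that randomisation replaces adjustment in the analysis. The wording can equally mean ordinary balancing of the arms, and A.6.1 describes stratification that way. It is worth clarifying but is not an error in itself. Nor does the plan say that follow-up raters differ by site. It says that follow-up staff differ from baseline staff (A.6.1), and that assessments are filmed to support a uniform review (A.6.4).

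Two further objections stand in full. The loss is conditional on stratum effects that the documents do not quantify. It is also a loss relative to a better analysis, not to the plan's own calculation, which is framed as a plain comparison of two proportions.

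**Conclusion.** The point holds conditionally. Allocation is stratified by inhaler type within site, and the stated primary analysis carries no stratum term. If the strata are prognostic, an arm-only analysis gives a risk-ratio interval that is somewhat too wide and a test below its nominal 5%. The power given up is roughly 0-2 points with moderate strata and about 7 points with strong ones. If the strata are not prognostic nothing is lost, and a nine-cell analysis could cost about 2 points.

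These sizes rest on assumed stratum rates, three sites, permuted blocks of four, 20% random loss and a two-sided 5% test.

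Two stronger conclusions are not supported. Type I error is not inflated: the error is on the safe side. And adjustment does not rescue the sample size, since power stayed below 80% in every scenario examined. The mismatch between 80 subjects and the stated power is a separate and larger problem.

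**What to change.** In A.7, state that the primary risk ratio, its 95% confidence interval and the test account for the randomisation factors, and name one method. Suitable choices are:

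- A Mantel-Haenszel risk ratio with a Cochran-Mantel-Haenszel test, stratified by inhaler type. In the simulations this gained as much as nine cells or slightly more, with far less sparsity.
- The same over inhaler type by site, with single-arm cells contributing nothing.
- Logistic regression with inhaler type and site as main effects, and a standardised risk ratio (mean predicted success under each arm over all assessed subjects) with a stated interval method. This keeps both factors, but its test ran at up to about 6% in the simulations.

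Do not write a rule that drops site once a single-arm cell appears. Step 6 shows that it could be triggered often, which would leave the primary analysis to depend on who happened to be assessed.

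Optionally, reword the A.7 rationale to say that stratified randomisation balances these factors and the analysis adjusts for them. Align the synopsis.

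The cost is one or two sentences and no new data, because both factors are known at randomisation. The change should be made before outcome data by arm are seen, under the amendment rules in A.9.

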The investigational device is a separate module, inhalation app-module, embedded in the Cloud-based CE-marked system called AsthmaTuner. Our hypothesis is that provided education and training with the medical device measurement will improve the patients' ability to correctly use their inhalers over time. Thus, the aim of this study is to assess the effect of app-based medical device for education and training on inhalation techniques at 6-12 weeks follow-up visit in subjects with asthma and COPD. Secondary aim is to evaluate if the medical device is feasible to use in clinical practice. The study endpoints are peak inspiratory flow (PIF), time to PIF, flow (litre per min), inhalation time (seconds) and breath hold (seconds) divided by DPI and MDI, together with assessment of how the patient handles their inhaler according to a set of critical criteria. Patients treated for COPD or asthma in primary or secondary care will be invited to participate in a two-armed stratified randomised controlled blinded study (RCT) over 6-12 weeks.

The patient will download AsthmaTuner to their smartphone that connects to a Bluetooth spirometer (in this study, MIR AsthmaTuner). Inhalation test through Airflow Trainer, an adjustable resistance mounted on the home spirometer (Airflow Trainer), determines if the inhalation flow agrees with the endpoints for the inhaler used by study subject. The expected results of this trial will allow us to determine if app-based inhalation device improves inhalation technique compared with standard care. The goal of this project is to provide sufficient information for a CE-marked product of the inhalation app-module. The study will be performed by Karolinska Institutet (KI), [name] research group, also being the sponsor, but supported technically and intellectual expertise from Astra Zeneca and MediTuner AB (the owner of AsthmaTuner).

A.1.2 Identification of the clinical investigation plan

Title: App-based medical device for education and training of inhalation technique

Acronym: APPETITE

(Svensk titel): App-baserad medicinteknisk produkt för utbildning och träning av inhalationsteknik

Clinical investigation plan code: 02

CIV-ID: 23-06-043273

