A.4.E Steps that will be taken to control or mitigate the risks

The signed IB including the risk analysis shows all risk control options that have been implemented to mitigate the risks associated with the inhalation module.

A.4.F Rationale for benefit-risk ratio

The assumption is that the benefits of using the investigational device to improve inhalation technique in subjects with asthma and/or COPD compared with standard education outweigh the risks. The nature of the risk control options makes that there are no unacceptable residual risks, as all risks are identified as low. The expected benefit of the investigational medical device is to make materials and methods for training and education of inhalation technique more available and feasible to use for patient and HCP. Additionally, to make the support for inhaler use more accessible for patients at home or whenever patients feel inhalation support is needed. It is therefore that the manufacturer believes that the investigational device has a positive benefit-risk ratio and is safe to use for patients. However, the results of this clinical investigation will be considered, and the benefit-risk ratio will be reassessed after the clinical investigation has been completed.

A.5 Objectives and hypotheses of the clinical investigation

Our hypothesis is that the app-based investigational medical device consisting is superior for education and training of inhalation techniques in patients with asthma and COPD compared with standard care. The pre-clinical evaluation indicated the use of the investigational device is a feasible and safe for patients using inhaler(s) for treatment. The study assumption is that the investigational medical device will improve the relative rate of successful inhalation technique with at least 25% compared with control group.

Primary aim: To investigate if app-based education and training of inhalation technique improves the rate of successful inhalation techniques compared with control group at 6-12 weeks follow-up visit.

Secondary aims: To evaluate the usability and safety of the investigational device during the study period.

The claim that this clinical data can substantiate is: the inhalation app-module in AsthmaTuner is superior for education and training of inhalation techniques in patients with asthma and COPD, when compared to standard care.

There are no identified risks or anticipated adverse events that will be studied in this clinical investigation.

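### A.7 asks for a risk ratio from logistic regression, whose exponentiated coefficient is an odds ratio, and names no step between them; at the planned rates the two are 1.5 and 3.0

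*Protocol*

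**What the plan says.** The primary analysis paragraph of A.7 says that the effect on the rate of successful inhalation technique will be "determined across randomisation groups with logistic regression analysis as risk ratio (RR) with 95% confidence interval". This fixes both a model and an effect measure. The synopsis (A.1.5, Analysis) names the model only: "The effect of using the inhalation app-module will be analysed with logistic regression analysis across randomisation groups". The protocol mentions no odds ratio, log-binomial model, modified Poisson model, standardisation or other route from the logistic fit to a risk ratio and its interval.

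The decision rule in A.7 is worded as "If the number of patients with inhalation technique deemed for correction differ significantly between intervention and control group at 5% significance level" and does not name the test.

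The planning figures are 75% versus 50% in the synopsis, and 50% plus 25 points absolute with 20% dropout among 80 enrolled in A.7. A.5 instead speaks of a relative improvement of at least 25%.

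On the use of the result, A.4.F says that "the benefit-risk ratio will be reassessed after the clinical investigation has been completed", and A.1.1 says: "The goal of this project is to provide sufficient information for a CE-marked product of the inhalation app-module".

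On the design, A.6.4 stratifies the randomisation "into three groups of DPI, MDI or both DPI and MDI devices of four block numbers in each stratum per investigational site". A.7 explains: "The purpose of stratified block randomisation per investigational site is to adjust for imbalance in" subjects' acquired knowledge, device-related errors and assessors' review.

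**The concern.** An odds ratio approximates a risk ratio only when the outcome is uncommon. Here success is expected in half to three quarters of subjects. An analyst who follows A.7 literally could fit the logistic model, exponentiate the treatment coefficient and print it as RR. A 50% relative gain would then appear as a tripling, with an interval stretched in the same way.

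What is at stake is the reported size of the primary effect in a trial that A.6.1 calls confirmatory. The size matters beyond the 5% test, because the results feed a reassessment of benefit and risk and are meant to support CE marking.

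**Working it through.** **Inputs.** Success rates p1 = 0.75 (intervention) and p0 = 0.50 (control) come from A.1.5 and A.7. Enrolment is 80, allocated 1:1, with 20% dropout (A.7): 80 × 0.8 = 64 evaluable, or 32 per arm. I take these as given; the point does not depend on how the sample size was derived.

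**1. The two measures at the planned rates.** The protocol prints no planned risk ratio, so it has to be derived.
- RR = p1/p0 = 0.75/0.50 = 1.5
- OR = [p1/(1 − p1)]/[p0/(1 − p0)] = (0.75/0.25)/(0.50/0.50) = 3.0
- OR/RR = (1 − p0)/(1 − p1) = 0.50/0.25 = 2.0

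The raw logistic coefficient is ln 3 = 1.10; its exponent is 3.0. Fitting a logistic model to data with exactly these rates returns 3.00.

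**2. The relative reading in A.5.** A 25% relative gain on 50% is 62.5%.
- RR = 0.625/0.50 = 1.25
- OR = (0.625/0.375)/1 = 1.67
- OR/RR = 0.50/0.375 = 1.33

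**3. Intervals at 24/32 versus 16/32 (after 20% dropout).**
- SE(log RR) = √(1/24 − 1/32 + 1/16 − 1/32) = 0.204, so RR 1.50 (95% CI 1.01 to 2.24)
- SE(log OR) = √(1/24 + 1/8 + 1/16 + 1/16) = 0.540, so OR 3.00 (1.04 to 8.65)
- Risk difference 25 points (2 to 48)

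**4. Intervals at 30/40 versus 20/40 (no dropout).** RR 1.50 (1.05 to 2.15); OR 3.00 (1.16 to 7.73).

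**5. Can A.7 be carried out as a risk ratio?** Yes. At 24/32 versus 16/32, marginal standardisation of the logistic fit (delta method) and modified Poisson regression with robust standard errors both give RR 1.50 (1.005 to 2.238). At 30/40 versus 20/40, both give 1.50 (1.049 to 2.145).

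**6. Does the choice change the decision?** Both measures equal 1 under the null hypothesis. At 24/32 versus 16/32, p = 0.042 (logistic) and 0.047 (modified Poisson). At 30/40 versus 20/40, p = 0.023 and 0.026. I enumerated all two-arm binomial outcomes at 75% versus 50%, using Wald intervals and leaving out outcomes where an arm has no successes or all successes. The odds-ratio and risk-ratio intervals disagree on excluding 1 in 4.0% of trials with 32 per arm and in 0.9% with 40 per arm.

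**The case against.** The strongest reply is that A.7 contains no error. It names the scale (risk ratio) and the model (logistic), and a valid route between them exists, as step 5 shows. How the ratio is extracted is a detail that a protocol commonly leaves to the SAP, which is not at hand. In addition, if the arm-level success rates are reported, an RR of 3.0 beside 75% and 50% would be visibly wrong. Much of this stands, and it limits the point to a sentence that invites mislabelling. It does not remove the point, because the protocol is not silent: it commits to a pairing that the named model does not produce directly, for the primary endpoint.

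Three stronger readings are tempting, and the documents support none of them.

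- A reader might infer that the sponsor will report an odds ratio as a risk ratio. Nothing in the protocol says so.
- A reader might infer that the superiority test is compromised. The null value is 1 on both scales, and the claim in A.5 is one of superiority, with no threshold on the risk-ratio scale. No passage sets such a threshold for benefit-risk or CE marking either, so the link to those uses is a reason for care and not a demonstrated harm.
- A reader might put the overstatement at about 2.5. That is the median OR/RR among statistically significant trials at 75% versus 50% with 32 per arm, so it mixes the difference in scale with selection of large effects. The scale difference at the planned rates is 2.0.

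**Conclusion.** The point holds in a limited form. A.7 pairs logistic regression with a risk ratio and leaves the step between them unstated. If the exponentiated coefficient is labelled RR, the reported effect is overstated by a factor of 2.0 at the planned rates (3.0 for 1.5), or 1.33 on the A.5 reading (1.67 for 1.25), and the interval is overstated with it. The test of no difference is essentially unaffected, although the two intervals can occasionally fall on different sides of 1.

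The sizes rest on the protocol's planning rates and, for the intervals, on 32 or 40 evaluable subjects per arm. The harm is conditional on mislabelling, and an SAP that names the method would remove it. The wording should be corrected because it concerns the primary endpoint and costs almost nothing to change.

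**What to change.** Keep the risk ratio and name its method in A.7. Suggested text:

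> The risk ratio and risk difference for successful inhalation technique, with 95% confidence intervals, will be obtained by marginal standardisation of the logistic model (delta-method or bootstrap interval).

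Modified Poisson regression with robust standard errors is an equally acceptable alternative. If the logistic coefficient itself is to be reported, call it an odds ratio. State whether the logistic test or the risk-ratio interval carries the 5% decision, and align the synopsis.

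As a free improvement, and not as the correction of an error, include the randomisation stratum inhaler type (DPI, MDI or both) as a model term. A.7 gives adjustment for imbalance as the purpose of the stratification, but it does not promise covariates. Add site only if the data are not too sparse. Once a covariate is in the model, the exponentiated treatment coefficient is an odds ratio conditional on it, which is a further reason to state the standardisation step.

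The cost is a sentence or two in A.7. No further data are needed, since inhaler type and site are known at randomisation.
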